6.6.3.3. OS for Phase I

OS analyses will be performed in patients from the FAS.

The number of overall censored patients, number of patients with events and Kaplan-Meier estimates median time will be provided with 25th percentile and 75th percentile and 95% Confidence Interval.

In addition, the results will be presented graphically in Kaplan-Meier plots including count for numbers of patients at risk.

In addition, OS rates at different time points (every 6 months) will be estimated with corresponding 2-sided 95% CIs.

Frequency (number and percentage) of patients with an event (death) and censoring reasons will be presented by treatment group. Censoring reasons are as follows:

- Alive
- Withdrawal of consent
- Lost to follow-up

Lost to follow-up will include patients that the investigator states were lost to follow-up prior to the analysis cut-off.

OS values will be also presented in a data listing.

6.6.3.4. Duration of Complete Remission for Phase II

Duration of CR is defined only for patients who achieve CR after hu3F8-BsAb and will be calculated from the time of remission by cancer type group in patients from the FAS.

The number of overall censored patients, number of patients with events and Kaplan-Meier estimates median time will be provided with 25th percentile and 75th percentile and 95% Confidence Interval. In addition, the results will be presented graphically in Kaplan-Meier plots including count for numbers of patients at risk. Reasons for censoring will also be provided.

Duration of CR will also be presented in a data listing.

6.6.3.5. ORR for Group 2 of Phase II

ORR for patients from group 2 will be analyzed as ORR for patients from group 1 (See section 6.6.1.1) in the FAS.

The number and percentage of responder patients (Yes/ No) with details by best response categories (CR, PR versus Stable Disease, Progressive Disease, Not Evaluable, Missing) will be described in the FAS and the two-sided 90% and 95% confidence intervals using the Wilson's method will be provided.

In addition, overall responses at each cycle excluding potential response assessments after initiation of any new prohibited anticancer treatment will be provided with the 90% and 95% confidence intervals using the Wilson's method.

Patients whose CRF response is "Very Good Partial Response" will be considered as "Partial Response" for the analyses.

ORR values will be also presented in a data listing as well as overall responses at each cycle.

6.6.3.6. HAHA for Phases I and II

HAHA will be measured as previously described. The proportion of patients developing HAHA response (Positive / Negative) after hu3F8-BsAb therapy, as well as the continuous titer will be summarized at each timepoint for patients from the Safety Analysis Set.

In addition, HAHA data will be listed based on the Safety Analysis Set.

6.6.3.6.1. Additional analyses HAHA for Phase I

HAHA titer value over time will be presented graphically with time of dosing for patients in the Safety Analysis Set.

In addition, the correlation between HAHA response and ORR after cycle 4 (for neuroblastoma patients) will be analyzed using a logistic regression with inclusion of log(therapeutic dose) as a covariate and whether patients have HAHA at any point up until the last pre-dose HAHA assessment before cycle 4. If patients have switched dose after cycle 2, the average therapeutic dose will be used.

Similar analysis will be performed with DCR after cycle 4 (for osteosarcoma patients).

The association between HAHA and OS and PFS up to 4 months will be analysed by cancer type group using Cox-Regression analyses with log(therapeutic dose) and HAHA (Yes/ No) as time-dependent covariates. These analyses will be based on patients from the FAS.

This information will be summarized separately by cancer type in patients.

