13 CRITERIA FOR REMOVAL FROM STUDY

- **13.1** Patients come off treatment if there is PD at any time. Best clinical judgment will be used to determine whether a patient must undergo tests between cycles to make sure disease is not progressing. Patients are followed for toxicities for 30 days from last treatment.
- 13.2 Patients come off treatment if they have DLT (during cycle 1 of phase I) or life-threatening toxicity clearly attributable to hu3F8-BsAb. Patients in the first stage of phase I (one patient per dose level cohort) who experience ≤ grade 2 toxicity, will not come off treatment but can continue at the same dose if they do not experience DLT and if toxicity subsides to <grade 2 within 35 days of dose 1 of Hu3F8-BsAb.

- **13.3** Patients who become pregnant during the study must be withdrawn from treatment
- **13.4** The investigators will make every reasonable effort to keep each patient in the study until all planned treatments and assessments have been performed. The investigators may discontinue study drug treatment for the following reasons:
 - Adverse events, including unacceptable toxicity or exacerbation of underlying disease, associated with study drug administration and necessitating discontinuation of treatment. Patients who are coming off treatment due to adverse events will be treated and followed according to established, acceptable medical practice. All pertinent information concerning the outcome of such treatment will be entered in the MSKCC institutional Clinical Research Database (CRBD). Patients will be followed until resolution or stabilization of the adverse event.

13.5 Off Study Criteria:

- Thirty days after the last dose of study drug for patients coming off treatment due to DP
- For patients coming off treatment due to adverse events, patients will be followed until the date the event returns to baseline or <Grade 3 (whichever is higher) or the date patients start another treatment, whichever is earlier.
- Death
- Lost to follow-up
- Withdrawal of consent. The patient's desire to withdraw from the study may occur at any time. The investigator should carefully consider whether the patient's withdrawal of consent is due to an adverse event, and if so, record the adverse event as the reason for withdrawal.
- Withdrawal by the physician for clinical reasons not related to study drug treatment in the absence of an adverse event.

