2.1.1. Phase I

2.1.1.1. Phase I Design

Initially the phase I trial will follow a dose-escalation schema with 1 patient assigned per dose until the first \geq Grade 2 toxicity (except for Grade 2 sinus bradycardia, sinus tachycardia, urticaria, fever, nausea, vomiting, diarrhea, urticaria, headache, paresthesia, electrolyte disturbances, pain) is observed, then the subsequent dose allocation will follow the Continual Reassessment Method (CRM)^{1,2}. Eligible patients will include relapsed or refractory NB, osteosarcoma, and GD2 (+) solid tumors. In each cycle, hu3F8-BsAb is given on Days 1 and 8. PK is assessed by blood draws. Patients are monitored for Dose Limiting Toxicity (DLT) until Day 28. Patients with DLT will come off treatment. Human Anti-Human Antibody (HAHA) titer will be measured after each cycle. Extent of disease evaluation will be performed after the second dose of cycle 2 and cycle 4, then every 3 months thereafter. A total of 4 cycles will be given.

If patients experience no life-threatening toxicity clearly attributable to hu3F8-BsAb, do not develop progression of disease and continue to meet all eligibility criteria, they have the option of receiving additional cycles up to 2 years from the start of hu3F8-BsAb treatment. Patients may continue therapy beyond 4 cycles even if they achieve remission (see Figure 1). The duration of each subsequent cycle is 28 days with hu3F8-BsAb being given on Days 1 and 8. MTD is defined as the dose level that leads to DLT in approximately 15% of patients (posterior probability of DLT that comes closest to the toxicity level of 0.15). The RP2D will be decided based on the safety data in the phase I and can be MTD or lower. If MTD is not reached, RP2D may be determined on the basis of PK studies. If no DLT is observed, the RP2D will be determined as a minimum dose that gives the highest hu3F8-BsAb serum levels based on the PK data. For example, the RP2D of hu3F8 monoclonal antibody was decided as 9 mg/kg/cycle because the serum hu3F8 levels reached a plateau beyond 8.4 mg/kg/cycle with no DLT (see Protocol Section 3.2.3). After cycle 2, intra-patient dose escalation will be permitted i.e. patients can receive the highest dose that has been evaluated and proven safe by DLT assessment.

Figure 1 Trial Design

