5.2. Handling of Dropouts, Missing Data, and Outliers

5.2.1. Handling of Missing Efficacy Data

Patients with missing data for ORR analysis will be treated as non-responders. Additionally, for PFS analyses, patients without or missing evaluable tumor scan assessment will be censored as described in section 2.4.2.2.

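### The Phase I HAHA logistic models count HAHA at any time before Cycle 4 with no landmark, so the odds ratio is biased above 1 under no effect and cannot be interpreted

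*SAP*

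**What the plan says.** SAP 6.6.3.6.1 plans a logistic regression of response after Cycle 4 in neuroblastoma patients. The HAHA variable is "whether patients have HAHA at any point up until the last pre-dose HAHA assessment before cycle 4". Log therapeutic dose is a covariate: "If patients have switched dose after cycle 2, the average therapeutic dose will be used". A parallel model uses disease control after Cycle 4 for osteosarcoma. The only population named in that part of the section is the full analysis set: "These analyses will be based on patients from the FAS". No landmark, at-risk restriction or adjustment for number of samples is given.

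Four other provisions matter:

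- **Progression:** "Patients come off treatment if there is PD at any time" (Protocol section 13). Study participation then ends: "Thirty days after the last dose of study drug for patients coming off treatment due to DP" (DP is read here as progressive disease).
- **Missing response:** "Patients with missing data for ORR analysis will be treated as non-responders" (SAP 5.2.1).
- **Dose:** "After cycle 2, intra-patient dose escalation will be permitted" (SAP 2.1.1.1), so only patients still on treatment can have an escalated dose.
- **Sampling:** Protocol 10.13 draws HAHA before each cycle. Protocol 4.1.1 and 9.1.1 speak of a titer after each cycle.

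For OS and PFS, the same SAP section enters HAHA and log dose as time-dependent covariates in Cox models.

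**The concern.** An ever-positive variable depends on how often the patient was sampled. A patient who progresses at the Cycle 2 evaluation is a non-responder and leaves with one or two post-treatment samples; a patient who stays to Cycle 4 has three. The three-monthly follow-up draws do not make up the difference for progressors, because they stop when the patient goes off study. The groups being compared therefore differ in their opportunity to test positive, even if HAHA and response are unrelated. This is immortal-time bias. The Cox models in the same section avoid it and the logistic models do not.

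Evaluating HAHA is a Phase I secondary objective, and Protocol 14.3.2 lists HAHA induction among parameters that might predict response and survival. A spurious favourable association could be reported in that light. No dose decision, success rule or Phase II primary endpoint depends on this model.

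**Working it through.** The plan states no effect size, power or sample size for this analysis, so there is no figure of its own to reproduce.

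**Simple calculation with no true effect.** Assumptions, none from the documents: HAHA is found with probability q = 0.1 to 0.3 at each of the draws before Cycles 2, 3 and 4; responders have all three draws; a fraction f = 0.5 or 0.8 of non-responders leaves at Cycle 2 with k draws. k = 1 means the pre-Cycle 2 draw only; k = 2 adds one end-of-cycle sample.

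- Responders positive: 1 − (1 − q)^3
- Non-responders positive: f × [1 − (1 − q)^k] + (1 − f) × [1 − (1 − q)^3]

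Example with q = 0.2, f = 0.8, k = 1. Responders: 1 − 0.512 = 0.488, odds 0.953. Non-responders: 0.8 × 0.2 + 0.2 × 0.488 = 0.2576, odds 0.347. Odds ratio 0.953 / 0.347 = 2.75. The true value is 1.

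| q | k=2, f=0.5 | k=2, f=0.8 | k=1, f=0.5 | k=1, f=0.8 |
|---|---|---|---|---|
| 0.1 | 1.24 | 1.43 | 1.63 | 2.40 |
| 0.2 | 1.29 | 1.52 | 1.82 | 2.75 |
| 0.3 | 1.37 | 1.64 | 2.09 | 3.24 |

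For disease control, failure is largely progression, which itself stops treatment, so f may approach 1. At q = 0.2 and f = 1 the odds ratio is 0.953 / 0.5625 = 1.7 (k = 2) or 0.953 / 0.25 = 3.8 (k = 1).

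**Simulation of the full logistic model.** Response was independent of HAHA and dose. Further assumptions: response rate 25% (the Phase II null rate for neuroblastoma); HAHA onset 10%, 20% or 30% per cycle; 10%/20%, 15%/40% or 20%/60% of non-responders leaving in Cycle 1 / at the Cycle 2 scan; starting dose uniform over levels 5-12; escalation of 0-3 levels after Cycle 2.

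| Quantity | Pre-dose samples only | One extra sample for leavers |
|---|---|---|
| HAHA odds ratio | 1.41 to 4.19 | 1.19 to 1.91 |
| False-positive rate, N=30 | 8-40% | 7-13% |
| False-positive rate, N=15 | 10-25% | 10-13% |

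- With no early dropout the HAHA odds ratio is 1.00, which isolates the cause.
- The dose odds ratio is 1.07 to 1.20 per log unit against a true 1.00. In the middle scenario, using starting dose instead of average dose returns it to 0.99 but leaves the HAHA odds ratio at 2.24 (2.17 with average dose).
- A landmark at the pre-dose Cycle 2 sample, with starting dose, gives a HAHA odds ratio of 0.97 to 1.02 and a dose odds ratio of 1.00 in every scenario. Its false-positive rate is 4-9% at N=30 and 5-10% at N=15, so part of the excess over 5% above is small-sample error of the likelihood-ratio test.

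**Opposing mechanism.** If HAHA deferral turns 20%, 40%, 60% or 80% of HAHA-positive responders into non-responders, the middle-scenario odds ratio of 2.17 becomes 1.60, 1.07, 0.65 or 0.30.

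**The case against.** The strongest counter-argument is that HAHA can itself create non-responders. SAP 2.1.1.6 allows cycles to be delayed by up to 120 days for a titer above 1300 U/ml, the Cycle 4 scan window is 122 ± 30 days (SAP 5.1.4), and a missing response counts as failure. This stands. A reader might infer that the model will show HAHA as favourable; the documents do not support that, because the net direction cannot be derived from them. But deferral is no safeguard: an estimate that mixes a possible real effect with an artefact of opposite sign cannot be read.

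Other points also stand in part:

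- The higher figures need leavers to have only one sample. If end-of-cycle titers are taken, the lower range applies.
- Best response runs from the start of treatment (SAP 2.5.1.3), so a Cycle 2 responder who then stops, for example for toxicity, counts as a responder with fewer draws. That narrows the contrast.
- A reader might infer that averaged dose drives the HAHA result. It does not: averaging applies only to patients who switched, and it moves mainly its own coefficient.
- A reader might infer that the SAP introduced the problem by replacing the chi-square test. Protocol 14.1.2.2 set no landmark or at-risk restriction either. The SAP inherited the gap and did not close it when it rewrote the analysis.
- Restricting the model to patients who reach Cycle 4 also gave an odds ratio of 1.00 in the middle scenario, but the SAP names the full analysis set and states no such limit.

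**Conclusion.** The concern holds as a bias in the ever-positive HAHA definition. Under no true effect the HAHA odds ratio lies above 1: about 1.2 to 1.6 if leavers have two samples and 1.6 to 3.2 if they have one, on assumed rates of 10-30% HAHA per draw and 50-80% of non-responders leaving at Cycle 2. The reading that the model will show an association where none exists goes too far. In most simulated trials of this size the bias did not reach significance, its size rests on rates that the documents do not give, and deferral may offset or reverse it. What can be said is that the sign cannot be predicted and the estimate cannot be interpreted. The dose covariate is a lesser, separate issue. The importance is low: this is an additional Phase I analysis, split by tumor type, within up to 30 patients.

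**What to change.** In SAP 6.6.3.6.1, pre-specify a landmark analysis for both the response and disease-control models. Include patients still on treatment at the landmark, use HAHA status up to that draw, and use the log of the dose assigned at the start as covariate. The pre-dose Cycle 2 sample is the simplest landmark because it precedes the scheduled response assessments. State whether a patient whose Cycle 2 is deferred at that point counts as still on treatment. If the Cycle 2 disease evaluation is preferred as the landmark, state how responses already reached there are counted. State also which HAHA samples enter the model, given the before-cycle and after-cycle wordings.

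The cost is a few sentences of SAP text. Patients who leave before the landmark, and HAHA that arises after it, are not used in an already small model. The planned HAHA summaries, listings and titer plots still report them.

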6.6.4. Sensitivity Analyses for the Secondary Efficacy Analysis

For ORR analysis of phase I and in group 2 of phase II, the ORR at the end of trial but before new prohibited anticancer therapy will be also studied and the two-sided confidences intervals (90% and 95%) using the Wilson's method will be provided.

6.6.5. Subgroup Analysis

Not applicable

6.6.6. Exploratory Analysis

6.6.6.1. OS for Phase II

OS is defined as the time from first dose of treatment until death from any cause. All deaths will be included, whether they occur during the trial or following treatment discontinuation.

Data will be presented by cancer type (NB versus Osteosarcoma) based on the FAS.

The number of overall censored patients, number of patients with events and Kaplan-Meier estimates median time will be provided with 25th percentile, 75th percentile and 95%

Confidence Interval. In addition, the results will be presented graphically in Kaplan-Meier plots including count for numbers of patients at risk.

In addition, OS rates at different time points (every 6 months) will be estimated with corresponding 2-sided 95% CIs.

Frequency (number and percentage) of patients with an event (death) and censoring reasons will be presented by treatment group. Censoring reasons are as follows:

- Alive
- Withdrawal of consent
- Lost to follow-up

Lost to follow-up will include patients that the investigator states were lost to follow-up prior to the analysis cut-off.

OS values will be also presented in a data listing.

6.6.6.2. PFS for Group 1 of Phase II

PFS will be defined as the time from first dose of treatment to the earliest documented date of disease progression, or death due to any cause, whichever occurs first.

The number of censored patients, number of patients with events and Kaplan-Meier estimates median time will be provided with 25th percentile and 75th percentile and 95% Confidence Interval. In addition, the results will be presented graphically in Kaplan-Meier plots including count for numbers of patients at risk.

Frequency (number and percentage) of patients with an event (progression or death) and censoring reasons will be presented by treatment group. See section 2.4.2.2 for details of censoring reasons.

PFS values will be also presented in a data listing.

6.6.6.3. Immunological effects of hu3F8-BsAb for Phases I and II

Biologic correlate studies include (1) host immunity, (2) host T cell cytotoxic capacity, and (3) T cell homing into the tumor.

The parameters measured for each patient under "host immunity" include:

- the induction of HAHA,
- the induction of Ab3,
- the induction of Ab3'.

Under "T cell cytotoxic capacity", the following measurements will be made:

- (1) cytokine profiles including IFN-y, IL-6, IL-8, IL-10,

- (2) changes in lymphocyte populations and their differentiation including CD3, CD4, CD8, Foxp3, CD127, CD45RA, CCR7, and
- (3) activation and exhaustion markers on T cells including CD25 and PD-1.

"T cell homing" will be tested by immunohistochemistry of tumor samples if available.

For phase I, spaghetti plots of available data will be performed based on patients from the Safety Analysis Set.

For phase II, available data will be described by dose group (Neuroblastoma vs Osteosarcoma) based on patients from the Safety Analysis Set.

Available data will be also presented in a data listing.

6.6.6.4. Tumor DNA, RNA for NB patients only for Phases I and II

For NB patients only: tumor DNA and RNA matched to normal RNA, will be archived to profile tumor gene aberrations and gene expressions as well as to test correlation with MRD.

This information will become relevant when combined with genome and expression data from current and future studies of hu3F8-BsAb.

Given the heterogeneity of the diagnosis and stage in this trial, this objective is exploratory. No formal statistical comparisons will be made.

Tumor DNA and RNA will be described in patients from the Safety Analysis Set.

Relevant, available data will be presented in summaries/listing if deemed applicable.

6.6.6.5. Stool Microbiome

Sequencing of stool microbiota will be performed and correlated with clinical and immunological response in patients from the Safety Analysis Set.

Relevant, available data will be presented in summaries/listing if deemed applicable.

6.6.6.6. DCR

DCR at the end of cycle 4 for patients from phase I will be estimated for each disease type and provided with 90% and 95% Confidence Intervals using Wilson's method, by treatment group in the FAS.

For patients from phase II, DCR analyses will be performed by group (NB versus Osteosarcoma) and two-sided 90% and 95% Confidence Intervals using Wilson's method will be provided.

DCR values will be also presented in a data listing.

6.7. Safety

6.7.1. Extent of Exposure

Duration of exposure will be defined in months as:

- If last dose is a priming dose, then:

Exposure (months) = ([date of last dose – date of first dose] + 7)/30.4375

- If last dose is a therapeutic dose, then:

Exposure (months) = ([date of last dose – date of first dose] + 21)/30.4375

Duration of exposure in days will be summarized for the Safety Analysis Set by treatment group and overall. Descriptive statistics will be presented for duration of exposure.

The duration of exposure will also be computed in weeks (dividing by 7 the above computations), and summarized by treatment group, in patients from the Safety Analysis Set for following variables:

- Duration as continuous (in weeks) using descriptive statistics
- Categorized by time intervals (<4 weeks, 4-<8 weeks, ...) for which frequency counts and percentages of patients will be provided.
- Descriptive statistics will also be summarized for the total number of cycles received per patient, the number of doses received at Day 1, the number of doses received at Day 8.

The total dose of treatment in mcg/kg taken over the trial duration will be calculated as the total sum of all infusions received during the trial.

The total dose of treatment in mcg/kg taken over the trial duration will be summarized alongside dosing changes for the Safety Analysis Set by treatment group and overall as:

• Descriptive statistics will be presented for total dose of treatment (sum of actual dose received).

A listing of overall treatment exposure data, including the first and last dates of treatment will be presented together with compliance for the Safety Analysis Set. Further, trial treatment infusion data will be listed for the Safety Analysis Set.

Treatment interruptions due to Covid-19 will also be described if applicable.

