2.1.2. Phase II

After RP2D is determined, a phase II trial will be carried out to assess the anti-tumor activity of hu3F8-BsAb. Two groups of patients will be studied: Group 1 will consist of patients with relapsed or refractory NB and Group 2 of relapsed or refractory measurable osteosarcoma. Hu3F8-BsAb is given on Days 1 and 8 of each cycle. The duration of each cycle is 28 days. However, cycles may be delayed for up to 56 days if >grade 2 toxicity is encountered.

HAHA titer will be measured after each cycle. If HAHA develops, cycles are deferred for up to 120 days until HAHA titer <1300 U/ml. Extent of Disease Evaluation (EOD) will be performed after the second dose of cycle 2 and cycle 4, then every 3 months thereafter.

A total of 4 cycles will be given, and patients with no life-threatening toxicity clearly attributable to hu3F8-BsAb, no progressive disease, continuing to meet all eligibility criteria and HAHA titer is <1300U/ml have the option of receiving additional cycles up to 2 years from the start of the Hu3F8-BsAb treatment. Patients may continue therapy beyond 4 cycles even if they achieve remission.

After cycle 4, duration between cycles can range from 28-120 days. Patients will undergo physical examination, Complete Blood Count (CBC) and complete chemistry and immune correlates will be tested as described in Protocol Section 10.

For Group 1, the overall response rate will be evaluated and is defined as the proportion of patients achieving Complete Remission (CR) or Partial Response (PR) based on revised International Neuroblastoma Response Criteria (INRC)³ as the best of the responses at the end of cycle 2 and cycle 4. (See Section 2.4.2.1) excluding potential response assessments after initiation of any new prohibited anticancer treatment).

For Group 2, 4-month Progression Free Survival (PFS) will be assessed and is defined as the proportion of patients who have not developed progressive disease nor died at the end of 4 months from the first dose of Hu3F8-BsAb. In addition, number of patients who have CR or PR as the best of the responses at the end of cycle 2 and cycle 4 will be determined. (see Section 2.5.2.2)

Hu3F8-BsAb is given IV over ~1-3 hours on Days 1 and 8 for each cycle.

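### As written, the SAP's rule for exposure in weeks divides months by 7, so every patient would fall in the under-4-weeks category

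*SAP*

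**What the plan says.** SAP 6.7.1 sets the unit at the start: "Duration of exposure will be defined in months as". Two formulas follow. If the last dose was a priming dose: "Exposure (months) = ([date of last dose – date of first dose] + 7)/30.4375". If it was a therapeutic dose: "Exposure (months) = ([date of last dose – date of first dose] + 21)/30.4375".

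The section then names a second unit: "Duration of exposure in days will be summarized for the Safety Analysis Set by treatment group and overall". No formula in days is given.

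A third unit follows: "The duration of exposure will also be computed in weeks (dividing by 7 the above computations". The values in weeks are to be summarised as a continuous variable and also grouped: "Categorized by time intervals (<4 weeks, 4-<8 weeks", and so on.

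Two other sections bear on the range of values. SAP 6.5 plans infusions on days 1 and 8 of 28-day cycles. SAP 2.1.1.1 limits optional further treatment in phase I: "they have the option of receiving additional cycles up to 2 years from the start of hu3F8-BsAb treatment". SAP 2.1.2 does the same for phase II: "have the option of receiving additional cycles up to 2 years from the start of the Hu3F8-BsAb treatment". The changes listed in SAP Section 7 do not mention exposure.

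**The concern.** The weeks rule refers back to computations that are already in months. Dividing a number of months by 7 has no meaning as a duration. The section names three units, writes a formula for one of them, and gives a conversion that does not work from that formula. The quantity the conversion needs, a day count, is named but not defined.

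At stake is the exposure-in-weeks summary by treatment group: its descriptive statistics and its four-week categories. A programmer who follows the text gets wrong values. One who corrects it silently departs from the plan, and two people working from the same text could produce different tables.

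**Working it through.** **Inputs**

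- Month formulas, SAP 6.7.1: (last dose date − first dose date + 7 or + 21)/30.4375.
- Weeks rule, SAP 6.7.1: the above divided by 7.
- First cut-point, SAP 6.7.1: 4 weeks.
- Doses on days 1 and 8 of 28-day cycles, SAP 6.5.
- Treatment limit of 2 years from first dose, SAP 2.1.1.1 and 2.1.2; taken here as 730 days.
- Assumption: the Day 1 dose is the priming dose and the Day 8 dose the therapeutic one. The added 7 and 21 days fit this, since 7 days run from Day 1 to Day 8 and 21 days from Day 8 to the start of the next cycle.

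The plan gives no worked value in weeks, so there is no stated figure to reproduce.

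**Formulas compared.** Let D = last dose date − first dose date + 7 or + 21, in days.

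- Literal: weeks = (D/30.4375)/7
- With consistent units: weeks = D/7
- Ratio of the second to the first: 30.4375, for every patient

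**Example, four cycles on schedule.** The Day 8 dose of cycle 4 falls 3 × 28 + 7 = 91 days after the first dose, so D = 91 + 21 = 112.

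- Literal: 112/30.4375 = 3.68 months; 3.68/7 = 0.53
- Consistent: 112/7 = 16.0

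**Range**

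| Situation | D (days) | Months | Literal (months/7) | D/7 (weeks) |
|---|---|---|---|---|
| One priming dose only | 0 + 7 = 7 | 0.230 | 0.033 | 1.00 |
| Cycle 1 complete | 7 + 21 = 28 | 0.920 | 0.131 | 4.00 |
| Cycle 2 complete | 35 + 21 = 56 | 1.840 | 0.263 | 8.00 |
| Cycle 4 complete | 91 + 21 = 112 | 3.680 | 0.526 | 16.00 |
| Last therapeutic dose 730 days after the first | 730 + 21 = 751 | 24.674 | 3.525 | 107.29 |
| Last cycle starts at 730 days, Day 8 dose follows | 737 + 21 = 758 | 24.903 | 3.558 | 108.29 |

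**Can anyone reach 4 under the literal rule?** It needs 4 × 7 = 28 months, that is 28 × 30.4375 = 852.25 days of exposure. The last therapeutic dose would have to come 852.25 − 21 = 831.25 days after the first, beyond the two-year limit even if a cycle begun at the limit is completed. So all patients land in the first category and every later one is vacant. Under D/7, a patient who receives both cycle 1 doses on schedule has exactly 4.00 weeks and already belongs in the second category.

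**The case against.** The strongest reply is that nobody would apply the rule literally. The sentence on exposure in days stands shortly before the weeks sentence, so the nearest named quantity is a day count. The bracketed numerator of each formula is that day count. Divided by 7, it lines up with the four-week cut-points: 28 days is 4.00 weeks and 56 days is 8.00. This stands as evidence of intent, and days/7 was probably meant. It does not make the written rule correct, because no day formula is given and the only computations above the sentence are in months.

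A second reply is that the error would show itself. About half a week of exposure for patients who completed four cycles would clash with the cycle and dose counts in the same summary and with the listed treatment dates. That also stands: an unnoticed wrong table is unlikely. The table shells to which SAP 6.1 refers are not among the documents and may state the right formula, so the programmed result cannot be predicted.

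A reader might infer that the safety results are distorted because exposure is their denominator. The SAP does not support that. The adverse event tables in 6.7.3 use numbers and percentages of patients and event counts, with no person-time rate. The DLT summary in 6.7.2 uses numbers and percentages of patients in the DLT evaluable set. Exposure in weeks enters neither.

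**Conclusion.** The weeks rule is wrong as written. Followed literally, it understates exposure in weeks by a factor of 30.4375 for every patient, and the four-week categories separate no one. They would not be empty: one would hold all patients. The factor follows from the formulas alone. The statement that every patient falls below 4 rests also on the two-year limit being observed.

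The reach is small. Only the descriptive summary of exposure in weeks is affected. The month formulas are sound, and the counts of cycles and doses, the total dose in mcg/kg and the listed dates do not use the division by 7. Adverse event and DLT rates, the MTD, ORR and PFS are untouched. It is a minor correction, worth making because the text and the probable intent differ and nothing else in the SAP resolves the difference.

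**What to change.** Rewrite the opening of SAP 6.7.1 so that days come first:

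- Exposure (days) = date of last dose − date of first dose + 7 if the last dose was a priming dose, or + 21 if it was a therapeutic dose.
- Exposure (months) = exposure (days)/30.4375.
- Exposure (weeks) = exposure (days)/7.

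Remove the reference back to the above computations, and check that the table shells carry the same three lines. This also supplies the missing definition for the summary in days. The cost is a few lines of SAP text, with no change to data collection, design or any other analysis.
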